1.1. Synopsis

Protocol Title: A Randomized, Double-Blind, Parallel Arm Study of the Efficacy and Safety of Two Doses of Dulaglutide in Combination with a Single Oral Antihyperglycemic Medication or as Monotherapy in Japanese Patients with Type 2 Diabetes Mellitus (AWARD-JPN: Assessment of Weekly AdministRation of LY2189265 in Diabetes – JAPAN)

Short Title: Efficacy and Safety of Two Doses of Dulaglutide (1.5 mg versus 0.75 mg) in Japanese Patients with Type 2 Diabetes (AWARD-JPN)

Rationale:

In Phase 3 confirmatory studies in Japanese patients with T2D (H9X-JE-GBDP and GBDY), once weekly (QW) dulaglutide 0.75 mg has shown non-inferiority to liraglutide 0.9 mg and superiority to insulin glargine in hemoglobin A1c (HbA1c) reduction (Araki et al. 2015; Miyagawa et al. 2015). Also, in a Phase 3 long-term safety study in combination with a single oral antihyperglycemic medication (OAM) (sulfonylurea, biguanides, α -glucosidase inhibitors, thiazolidinediones, or glinides) (H9X-JE-GBDQ) and in a Phase 4 study in combination with insulins (basal, mixed, or basal bolus) (H9X-JE-GBGF), it was shown that the anti-hyperglycemic effect of once-weekly dulaglutide 0.75 mg was sustained for the 52 week treatment period (Emoto et al. 2015; Ishii et al. 2020).

However, dulaglutide 0.75 mg may not be sufficient in some participants for achieving the target HbA1c value. In Japanese Phase 3 and Phase 4 studies of dulaglutide 0.75 mg (monotherapy, combination with OAM, and combination with insulin), the percentage of participants achieving the target HbA1c value $<7\%$ was 47.4% to 83.1%, and the percentage of participants achieving the target HbA1c value $\leq 6.5\%$ was 25% to 70.8%. That means there is some room to improve glycemic control with dulaglutide 0.75 mg and it is desired that the dose is increased to 1.5 mg, which is the most frequently prescribed dose worldwide.

The purpose of the proposed Phase 3 study (H9X-JE-GBGQ) is to assess the efficacy and safety of once-weekly (QW) dulaglutide 1.5 mg in comparison to dulaglutide 0.75 mg. The overall goal of this study is to gain regulatory approval for an additional dose of dulaglutide 1.5 mg in patients with T2D who require additional glucose control after treatment of dulaglutide 0.75 mg in Japan.

Objectives and Endpoints

Objectives	Endpoints
Primary	

 To demonstrate that once-weekly dulaglutide 1.5 mg is superior to dulaglutide 0.75 mg for change from baseline in HbA1c at 26 weeks 	
 Change from baseline in HbA1c at 26 weeks
Secondary	
Efficacy 
 To compare dulaglutide 1.5 mg to 0.75 mg for efficacy parameters through 26 and 52 weeks 	
 Change from baseline in HbA1c Proportion of participants achieving HbA1c target of $\leq 6.5\%$ and $< 7.0\%$ Change from baseline in FSG Change from baseline in 6-point SMBG Change from baseline in body weight
Safety 
 To compare dulaglutide 1.5 mg to 0.75 mg for safety parameters through 26 and 52 weeks 	
 Incidence of TEAEs Discontinuation of study intervention due to AEs Incidence of hypoglycemic episodes Change from baseline in vital signs (SBP, DBP, and pulse rate) Change from baseline in laboratory tests^a

Abbreviations: AEs = adverse events; DBP = diastolic blood pressure; FSG = fasting serum glucose; HbA1c = hemoglobin A1c; SBP = systolic blood pressure; SMBG = self-monitored blood glucose; TEAEs = treatment-emergent adverse events.

^a Specified in Section 10.2 (Appendix 2).

Overall Design

Study H9X-JE-GBGQ is a Phase 3, multicenter, randomized, double-blind, parallel-group study in participants with T2D with inadequate glycemic control on a single OAM.

The OAMs include:

- sulfonylureas (SU)
- biguanides
- alpha-glucosidase inhibitors (a-GI)
- thiazolidinedione (TZD)
- glinides
- sodium-glucose cotransporter type 2 inhibitors (SGLT2i), and

- DPP-4 inhibitors (DPP-4i).

In each arm,

If taking	then participants are required
DPP-4i	to stop DPP-4i at randomization Note: In case of weekly DPP-4i, it must be stopped 1 week before randomization.
other OAMs	to continue the same dose of OAM during the study period exception: dose modifications are allowed in the event of hypoglycemia

Abbreviations: DPP-4i = DPP-4 inhibitors; OAM = oral antihyperglycemic medication.

Switching from DPP-4i is regarded as monotherapy of dulaglutide and taking other OAMs is regarded as combination therapy with OAM.

Disclosure Statement: This is a parallel-group treatment with 2 arms that is participant and investigator blinded.

Number of Participants:

Approximately 585 participants will be enrolled and randomized in order to obtain approximately 528 evaluable participants at 26 weeks (176 evaluable participants for dulaglutide 0.75 mg group and 352 evaluable participants for 1.5 mg group). For sample size determination see Section 9.2.

The number of enrolled participants will be 225 participants for DPP-4i, and 60 participants per OAM class for other OAMs (360 participants for other OAMs in total).

Intervention Groups and Duration:

[figure not shown]
Participants will be randomized at Visit 3 in a 2:1 ratio to weekly subcutaneous injections of dulaglutide 1.5 mg or 0.75 mg.

The study will consist of 3 periods (See Section 1.2):

- an approximately 2-week screening/lead-in period
- a 52-week treatment period including Treatment Period I (26-week for the primary endpoint) and Treatment Period II (26-week), and
- a 4-week safety follow-up period.

Data Monitoring Committee: No

1.2. Schema

Abbreviations: a-GI = alpha-glucosidase inhibitors; DPP-4i = dipeptidyl peptidase-4 inhibitor; F/U = follow up; OAM = oral antihyperglycemic medications; pts = patients; SGLT2i = sodium-glucose cotransporter type 2 inhibitors; SU = sulfonylureas; T2D = type 2 diabetes; T/V = telephone visit; TZD = thiazolidinedione; w = week; QW = once weekly.

Note: Visit 2 (Week -1) and Visit 4 (Week 2) will be conducted as a telephone visit.

1.3. Schedule of Activities (SoA)

Study Schedule Protocol H9X-JE-GBGQ

Visit	Screening/ Lead-In		Treatment Period							Safety Follow- Up	Comments	
			Treatment Period I				Treatment Period II					
	1	2	3	4	5	6	7	8	9	ET	801	
Week of Treatment	-2	-1	0	2	8	16	26	38	52	ET	56	
Allowable Deviation (Days)	-7~+3	±3		±3	±7	±7	±7	±7	±7		±7	The visit date is determined in relation to the date of the randomization visit (± the allowed visit window).
Fasting visit			X		X	X	X	X	X	X		Participants should be reminded to report to the site in a fasting condition, after a period of approximately 8 hours without eating, drinking (except water), or any significant physical activity and before taking their OAMs (if used). If the participant is not fasting, the participant should be called in for a new visit within the visit window.
Telephone visit		X		X								
Informed consent	X											
Inform eligibility to participants		X										
Randomization			X									Baseline assessments must be completed before processing in the IWRS.
Physical examination	X		X		X	X	X	X	X	X		
Medical history (general)	X											
Height	X											
Weight	X		X		X	X	X	X	X	X		
Vital signs (sitting SBP, DBP, and PR)	X		X		X	X	X	X	X	X		For each parameter, 2 measurements will be taken using the same arm; the recordings should be taken at least 1 minute apart. (Section 8.2.2)
ECG	X		X				X		X	X	X	12-lead ECG (Section 8.2.3)
Adverse events	X	X	X	X	X	X	X	X	X	X		
Concomitant medications	X		X		X	X	X	X	X	X		
Hypoglycemic events			X	X	X	X	X	X	X	X		
Diabetes management education	X											All training should be repeated as needed to ensure participant compliance.
Dispense participant diary	X		X		X	X	X	X	X			
Review participant diary			X		X	X	X	X	X	X		

	Screening/ Lead-In		Treatment Period								Safety Follow- Up	Comments
			Treatment Period I				Treatment Period II					
Visit	1	2	3	4	5	6	7	8	9	ET	801	
Week of Treatment	-2	-1	0	2	8	16	26	38	52	ET	56	
Allowable Deviation (Days)	-7~+3	±3		±3	±7	±7	±7	±7	±7		±7	The visit date is determined in relation to the date of the randomization visit (± the allowed visit window).
Dispense BG meter/supplies	X		X		X	X	X	X	X			During the study period, the participants are required to measure their pre-breakfast BG concentration at least once a week and record the BG concentration in their study diary.
BG meter, SMBG training	X											All training should be repeated as needed to ensure participant compliance.
6-point SMBG values			X				X					6-point SMBG consists of measurements before and 2 hours after each of 3 main meals within the same day. These SMBG profiles will be collected by the participant twice (2 days) within 1 week prior to the assigned visits.
Dispense study intervention and/or injection supplies			X		X	X	X					
Injection training			X									All training should be repeated as needed to ensure participant compliance.
Observe participants inject study intervention			X									Participants should administer their first dose of study intervention at the end of this visit, after other study procedures and randomization.
Participants return study intervention and/or injection supplies					X	X	X	X	X			
Assess study intervention compliance					X	X	X	X	X			
Human chorionic gonadotropin (hCG)	X											Human chorionic gonadotropin (hCG) will be measured at Visit 1 for women of childbearing potential.
Follicle-stimulating hormone (FSH)	X											Follicle-stimulating hormone (FSH) will be measured at Visit 1 for potentially postmenopausal women.
Urine pregnancy test (local)			X		X	X	X	X	X			A local urine pregnancy test will be performed at Visit 3, with the result available prior to randomization and first injection of study intervention, and at additional visits as shown in the schedule, for women of childbearing potential only.
Hematology	X		X				X		X	X	X	
Clinical Chemistry	X		X				X		X	X	X	

	Screening/ Lead-In		Treatment Period							Safety Follow- Up	Comments	
			Treatment Period I				Treatment Period II					
Visit	1	2	3	4	5	6	7	8	9	ET	801	
Week of Treatment	-2	-1	0	2	8	16	26	38	52	ET	56	
Allowable Deviation (Days)	-7~+3	±3		±3	±7	±7	±7	±7	±7		±7	The visit date is determined in relation to the date of the randomization visit (± the allowed visit window).
Lipid panel	X		X				X		X	X	X	
Pancreatic amylase, lipase	X		X				X		X	X	X	
Calcitonin	X		X				X		X	X	X	
Urine chemistry	X		X				X		X	X	X	Urinary albumin and creatinine will be measured.
Urine albumin -to creatinine ratio (UACR)	X		X				X		X	X	X	
eGFR	X		X				X		X	X	X	eGFR: Calculated by the Japanese Society of Nephrology equation
Fasting serum glucose			X		X	X	X	X	X	X		
HbA1c	X		X		X	X	X	X	X	X		
Samples for storage			X				X		X	X		Plasma and serum stored samples. Additional samples may be collected at additional timepoints where required (in the event of severe hypersensitivity reactions such as anaphylaxis). See Section 8.3.3(f) and 8.9.

Abbreviations: BG = blood glucose; DBP = diastolic blood pressure; ECG = electrocardiogram; eGFR = estimated glomerular filtration rate; ET = early termination; HbA1c = hemoglobin A1c; IWRS = interactive web-response system; OAM = oral antihyperglycemic medication; PR = pulse rate; SBP = systolic blood pressure; SMBG = self-monitored blood glucose.

2. Introduction

Dulaglutide (Trulicity®) is a once-weekly (QW) glucagon-like peptide-1 (GLP-1) receptor agonist (RA) that is approved for use as an adjunct to diet and exercise to improve glycemic control in patients with type 2 diabetes (T2D).

2.1. Study Rationale

In Phase 3 confirmatory studies in Japanese patients with T2D (H9X-JE-GBDP and GBDY), QW dulaglutide 0.75 mg has shown non-inferiority to liraglutide 0.9 mg and superiority to insulin glargine in hemoglobin A1c (HbA1c) reduction (Araki et al. 2015; Miyagawa et al. 2015). Also, in a Phase 3 long-term safety study in combination with a single oral antihyperglycemic medication (OAM) (sulfonylurea, biguanides, α -glucosidase inhibitors, thiazolidinediones, or glinides) (H9X-JE-GBDQ) and in a Phase 4 study in combination with insulins (basal, mixed, or basal bolus) (H9X-JE-GBGF), it was shown that the anti-hyperglycemic effect of QW dulaglutide 0.75 mg was sustained for the 52-week treatment period (Emoto et al. 2015; Ishii et al. 2020).

However, dulaglutide 0.75 mg may not be sufficient in some participants for achieving the target HbA1c value. In Japanese Phase 3 and Phase 4 studies of dulaglutide 0.75 mg (monotherapy, combination with OAM, and combination with insulin), the percentage of participants achieving the target HbA1c value $<7\%$ was 47.4% to 83.1%, and the percentage of participants achieving the target HbA1c value $\leq 6.5\%$ was 25% to 70.8%. That means there is some room to improve glycemic control with dulaglutide 0.75 mg and it is desired that the dose is increased to 1.5 mg, which is the most frequently prescribed dose worldwide. Dulaglutide 1.5 mg has shown greater reduction of HbA1c compared to 0.75 mg (Wysham et al. 2014, Giorgino et al. 2015, Umpierrez et al. 2014, Ludvik et al. 2018, Nauck et al. 2014) in Study GBDA, GBDB, GBDC, GBCF, and GBGE, which compared the efficacy and safety of both doses as monotherapy or combination with OAM.

2.2. Background

The global approved doses of dulaglutide (0.75 mg and 1.5 mg) were selected in the global Phase 2/3 study H9X-MC-GBCF (Skrivanek et al. 2014). The purpose of the phase 2 part of Study GBCF was to identify an optimal dose using prespecified measures of efficacy (HbA1c and weight) and safety (diastolic blood pressure and heart rate). The results determined that dulaglutide 1.5 mg was the optimal dose, and dulaglutide 0.75 mg met the criteria for the second dose (Skrivanek et al. 2014). Efficacy and safety of both dulaglutide 0.75 mg and 1.5 mg were investigated in global Phase 3 studies H9X-MC-GBDA, GBDB, GBDC, GBDD, and GBCF (Wysham et al. 2014, Giorgino et al. 2015, Umpierrez et al. 2014, Blonde et al. 2015, and Nauck et al. 2014), and both doses were approved in the US, EU, and other regions worldwide based on these study results.

In Japan, in a Phase 1 study of dulaglutide in Japanese patients with T2D (H9X-JE-GBCL), pulse rate increase (>5 bpm) was observed in the dulaglutide 1.0 mg and 1.5 mg treatment groups. Although there was no clinically significant safety issue observed in the study other than pulse rate increase, it was decided to investigate the lower dose (less than 1.0 mg) in a Phase 2

study in Japanese patients with T2D (H9X-JE-GBCZ). In the GBCZ study, dulaglutide 0.25 mg, 0.5 mg, and 0.75 mg were investigated and the greatest efficacy was observed in the dulaglutide 0.75 mg treatment group (Terauchi et al. 2014). In Phase 3 studies in Japanese patients with T2D (H9X-JE-GBDP, GBDY, and GBDQ), clinical efficacy and safety of dulaglutide 0.75 mg was investigated and dulaglutide 0.75 mg was approved in 2015 in Japan based on results from those clinical studies.

Pulse rate elevations are now recognized to be a class effect common to all GLP-1 RAs (Lorenz et al. 2017). Despite increases in pulse rate, completed cardiovascular outcome studies for GLP-1 RAs have shown either neutral or favorable effects on the risk of major cardiovascular events compared to placebo in patients with T2D and high cardiovascular risk (Pfeffer et al. 2015; Marso et al. 2016a; Marso et al. 2016b; Holman et al. 2017). Also, in Study GBDJ (REWIND), dulaglutide 1.5 mg reduced a composite of cardiovascular outcome (MACE-3; death from CV causes, nonfatal myocardial infarction, or nonfatal stroke) in T2D patients with high cardiovascular risk (Gerstein 2019).

The purpose of the proposed Phase 3 study (H9X-JE-GBGQ) is to assess the efficacy and safety of QW dulaglutide 1.5 mg in comparison to dulaglutide 0.75 mg. The overall goal of this study is to gain regulatory approval for an additional dose of dulaglutide 1.5 mg in patients with T2D who require additional glucose control after treatment of dulaglutide 0.75 mg in Japan.

2.3. Benefit /Risk Assessment

More detailed information about the known and expected benefits and risks and reasonably expected adverse events of dulaglutide may be found in the Investigator's Brochure (IB).

3. Objectives and Endpoints

Objectives	Endpoints
Primary	

 To demonstrate that once-weekly dulaglutide 1.5 mg is superior to dulaglutide 0.75 mg for change from baseline in HbA1c at 26 weeks 	
 Change from baseline in HbA1c at 26 weeks
Secondary	
Efficacy 
 To compare dulaglutide 1.5 mg to 0.75 mg for efficacy parameters through 26 and 52 weeks 	
 Change from baseline in HbA1c Proportion of participants achieving HbA1c target of $\le 6.5\%$ and $< 7.0\%$ Change from baseline in FSG Change from baseline in 6-point SMBG Change from baseline in body weight
Safety 
 To compare dulaglutide 1.5 mg to 0.75 mg for safety parameters through 26 and 52 weeks 	
 Incidence of TEAEs Discontinuation of study intervention due to AEs Incidence of hypoglycemic episodes Change from baseline in vital signs (SBP, DBP, and pulse rate) Change from baseline in laboratory tests^a

Abbreviations: AEs = adverse events; DBP = diastolic blood pressure; FSG = fasting serum glucose; HbA1c = hemoglobin A1c; SBP = systolic blood pressure; SMBG = self-monitored blood glucose; TEAEs = treatment-emergent adverse events.

^a Specified in Section 10.2 (Appendix 2).

4. Study Design

4.1. Overall Design

Study H9X-JE-GBGQ is a Phase 3, multicenter, randomized, double-blind, parallel-group study in participants with T2D with inadequate glycemic control on a single OAM. The OAMs include:

- Sulfonylureas (SU)
- biguanides
- alpha-glucosidase inhibitors (a-GI)
- thiazolidinedione (TZD)
- glinides
- sodium-glucose cotransporter type 2 inhibitors (SGLT2i), and
- DPP-4 inhibitors (DPP-4i).

Participants will be randomized at Visit 3 in a 2:1 ratio to weekly subcutaneous injections of dulaglutide 1.5 mg or 0.75 mg.

In each arm,

If taking	then participants are required
DPP-4i	to stop DPP-4i at randomization Note: In case of weekly DPP-4i, it must be stopped 1 week before randomization.
other OAMs	to continue the same dose of OAM during the study period exception: dose modifications are allowed in the event of hypoglycemia

Abbreviations: DPP-4i = DPP-4 inhibitors; OAM = oral antihyperglycemic medication.

Switching from DPP-4i is regarded as monotherapy of dulaglutide and taking other OAMs is regarded as combination therapy with OAM.

The study will consist of 3 periods (See Section 1.2):

- an approximately 2-week screening/lead-in period
- a 52-week treatment period including Treatment Period I (26-week for the primary endpoint) and Treatment Period II (26-week), and
- a 4-week safety follow-up period.

Screening (Visit 1)

At Visit 1, the investigator or site staff will initiate the assessment of participant eligibility for the study. The participant will sign the informed consent form (ICF) and receive a participant

identification number before any study procedures are performed. Procedures at Visit 1 will be performed as shown in the schedule of activities (SoA) (Section 1.3).

The participant and their caregiver(s) will be provided;

- diabetes management education
- glucometer and training on how to perform self-monitored blood glucose (SMBG)
- visit-specific diaries and training on how to record blood glucose (BG) values, OAM, hypoglycemic events, other concomitant medications, and adverse events (AEs).

During the screening/lead-in period, participants are required to continue their pre-study OAM therapy and should not change the type of OAMs used or their doses in order to allow reliable assessment of HbA1c at Visit 3.

Visit 2 (telephone visit)

At Visit 2, the investigator or site staff will inform participants of the screening results and instruct participants to perform the 6-point SMBG twice (2 days) before Visit 3.

In case of weekly DPP-4i, it must be stopped 1 week before randomization.

Visit 3

At Visit 3, participants should arrive at the study site in an at least 8-hour fasting state. In the fasted status, intake of water is allowed.

After confirming participant eligibility, participants will be randomized in a 2:1 ratio to weekly injections of dulaglutide 1.5 mg or 0.75 mg at Visit 3.

Randomization will be stratified by pre-study OAM class and HbA1c at Visit 1.

Stratification factors	Groups
pre-study OAM class	SU biguanides TZD a-GI glinides SGLT2i DPP-4i
HbA1c at Visit 1	low (<8.5% for DPP-4i class and <9.0% for other OAM classes) high ($\geq 8.5\%$ for DPP-4i class and $\geq 9.0\%$ for other OAM classes)

Abbreviations: a-GI = alpha-glucosidase inhibitors; DPP-4i = DPP-4 inhibitor; HbA1c = hemoglobin A1c; OAM = oral antihyperglycemic medications; SGLT2i = sodium-glucose, cotransporter type 2 inhibitors; SU = sulfonylureas; TZD = thiazolidinedione.

Participants will be instructed on how to use the Single-use pen and will inject their first dose of study intervention under the supervision of study personnel while in the clinic for Visit 3, after

randomization and other study procedures . The date and time of the first dosing of study intervention should be recorded on the eCRF.

Participants are required to continue using their concomitant OAMs, except for DPP-4i, throughout the treatment period. If a participant uses daily DPP-4i, it is required that the participants stop using daily DPP-4i at randomization.

Following randomization, participants will participate in a 52-week treatment period.

Treatment Period (Visit 3 to Visit 9)

Procedures during the treatment period will be performed as shown in the SoA (Section 1.3).

From Visit 3 through Visit 9 (except Visit 4), participants should arrive at the study site in an at least 8-hour fasting state. In the fasted state, intake of water is allowed.

Throughout the treatment period, participants will collect all of the following data in the participant diary:

- SMBG,
- dosing dates and time,
- hypoglycemic events,
- AEs, and
- concomitant medications.

The study site personnel will review the data at the next office visit.

At each office visit,

- study diaries will be collected,
- new study diaries will be dispensed (and instructions will be reviewed),
- used and unused study intervention and injection supplies will be returned, and
- new supplies will be dispensed as needed.

At Week 52 or the early termination (ET) visit, all used and unused study intervention will be returned.

Discontinuation or dose changes of concomitant OAMs are not permitted, except in certain situations (Section 6.5). Participants will be permitted to use concomitant medications that they require during the study, except certain medications that may interfere with the assessment of efficacy and safety characteristics of the study intervention (Section 6.5).

Safety Follow-Up Period

Procedures during the safety follow-up period will be performed as shown in the SoA (Section 1.3).

All participants who complete the treatment period (both I and II) are required to complete Visit 801, a safety follow-up visit approximately 4 weeks after the last visit of the treatment period. During the safety follow-up period, participants will not receive study intervention.

The safety follow-up period will also be applied to participants who discontinue from the study. In this case, the Safety Follow-Up visit (Visit 801) will occur approximately 4 weeks after the ET visit.

Participants are required to return any remaining study diaries to the study site at the end of this period.

Early Termination Visit

Every attempt will be made to keep participants in the study irrespective of their adherence to treatment with study intervention.

At any time after Visit 3 (randomization), a participant who is to discontinue from the study before Visit 9 will have an ET visit conducted. At this visit, procedures will occur as shown in the SoA (Section 1.3). Participants should be instructed to return any remaining used or unused study intervention supplies and diaries to the study site at this visit. Participants will be asked to perform the Safety Follow-Up visit (Visit 801) approximately 4 weeks after the ET visit, so that the Safety Follow-Up visit (Visit 801) will be their final visit. If the participant is not able to perform the Safety Follow-Up visit (Visit 801), the ET visit will be the final study visit. A participant summary electronic case report form (eCRF) will be completed.

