Calcitonin	Storage samples:
	Serum
	Plasma

^a Creatine kinase (CK) MB (CK-MB) is to be assayed if CK result >1000 IU/L.

^b eGFR will be calculated by the Japanese Society of Nephrology equation.

eGFR = $194 \times Cr^{-1.094} \times Age^{0.287}$
(male x1, female x0.739)

^c Calculated using the Friedewald equation. Reflex to direct LDL assay if triglyceride value >400mg/dL.

10.3. Appendix 3: Adverse Events: Definitions and Procedures for Recording, Evaluating, Follow-up, and Reporting

- The definitions and procedures detailed in this appendix are in accordance with International Organization for Standardization (ISO) 14155.
- Both the investigator and the sponsor will comply with all local medical device reporting requirements.
- The detection and documentation procedures described in this protocol apply to all sponsor medical devices provided for use in the study. See Section [6.1.1](#) for the list of sponsor medical devices.

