#### **Baseline definition**

Baseline will be defined as the last available value before the first injection for efficacy. In most cases, this will be the measure recorded at Baseline Visit 3 (Week 0). If the participant does not take any injection, the last available value on or prior to randomization date will be used. Change from baseline will be calculated as the visit value of interest minus the baseline value.

For the safety analyses, the following baselines will be used. For safety analyses using a baseline period, the baseline period is defined as the time from Screening Visit (Visit 1) to the date/time of the first injection.

- Treatment-emergent adverse events (TEAEs): baseline will be all results (including medical histories which are ongoing at the date of informed consent) recorded during the baseline period.
- Treatment-emergent abnormal laboratory and vital signs results: baseline will be all results recorded during the baseline period.
- Change from baseline to last post-baseline observation or to each scheduled post-baseline visit for laboratory and vital signs results: baseline will be the last scheduled non-missing assessment recorded during the baseline period.

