**[Case 2] Multiple post-baseline time point (e.g., Lab analysis from baseline through Week 52 and follow-up period)**

Change from baseline will be analyzed using mixed model for repeated measures (MMRM). Except for the HbA1c analysis (primary analysis), the model includes

- treatment, baseline value, visit, the interaction of treatment-by-visit, pre-study OAM class, and baseline HbA1c stratum,

as fixed effects.

The HbA1c analysis excludes the HbA1c stratification factor from the MMRM model because HbA1c is included as a continuous baseline variable.

The covariance structure to model the within-participant errors will be unstructured. If the unstructured covariance matrix results in a lack of convergence, the heterogeneous Toeplitz covariance structure, followed by the heterogeneous autoregressive covariance structure will be used. The restricted maximum likelihood (REML) will be used. The Kenward-Roger method will be used to estimate the denominator degrees of freedom.

Type III tests for the LS means will be used for the **treatment comparison**; LS mean difference, SE, p-value, and 95% CI will also be reported. In addition, **within treatment comparison** (the post-baseline value v.s. baseline value) will be conducted with the same model. P-value will be reported.

The same MMRM model will be used to estimate actual value at each visit.

For continuous laboratory analysis, the model specified above will be used for treatment comparison. However, actual visit values and change from baseline are based on descriptive statistics, not from the statistical models (LSmeans). There will be no within treatment comparison.

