##### TFLs Related to Clinical Laboratory Evaluations

Analysis	Additional Information
Listing of Patients with Treatment Emergent Abnormal (3*ULN) Laboratory Results	
Listing of Patients with Treatment Emergent Abnormal (ULN and LLN) Laboratory Results	
Summary and Analysis of Numeric Laboratory Tests	By Treatment Group and Visit
Summary and Analysis of Abnormal Laboratory Results	By Treatment Group and Visit
Shift of Calcitonin from Maximum Baseline to Maximum Postbaseline	By Treatment Group
Summary of Percent Change in Lipid Measurements	By Treatment Group and Visit

Abbreviations: LLN=Lower Limit Normal; ULN=Upper Limit Normal.

Listing of Individual Laboratory Values would be created upon request.

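### Visit 801 draws a lipid panel but is not a fasting visit, so Week 56 triglycerides and calculated LDL can show a fed-versus-fasting change that looks like drug withdrawal

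*Protocol*

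**What the plan says.** Protocol 4.1 sets the fasting rule for the treatment period: "From Visit 3 through Visit 9 (except Visit 4), participants should arrive at the study site in an at least 8-hour fasting state". The Fasting visit row of the schedule of activities (Protocol 1.3) is marked at Visits 3, 5, 6, 7, 8, 9 and ET, with the comment "Participants should be reminded to report to the site in a fasting condition, after a period of approximately 8 hours without eating". It is blank at Visits 1 and 801. The Lipid panel row is marked at Visits 1, 3, 7, 9, ET and 801.

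The Safety Follow-Up text in 4.1 refers to the schedule for procedures and adds no fasting instruction. It also states: "During the safety follow-up period, participants will not receive study intervention".

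On LDL cholesterol, footnote c of Protocol 10.2 says: "Calculated using the Friedewald equation. Reflex to direct LDL assay if triglyceride value >400mg/dL".

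The SAP provisions that bear on these samples are:
- Table GBGQ.3.1 includes the follow-up period in SS2, and 4.1.1 keeps follow-up data in the safety analysis by default.
- Section 4.1, Case 2, describes the laboratory model as "Multiple post-baseline time point (e.g., Lab analysis from baseline through Week 52 and follow-up period".
- The Baseline definition in 4.1 takes change from the latest scheduled value before the first injection. For abnormalities it uses a wider baseline: "Treatment-emergent abnormal laboratory and vital signs results: baseline will be all results recorded during the baseline period".
- Section 4.6.3.1 plans a "Summary of Percent Change in Lipid Measurements" by treatment group and visit, and listings of treatment-emergent abnormal results.

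**The concern.** Triglycerides depend on recent food, and a Friedewald LDL inherits that dependence because a fraction of the triglyceride value is subtracted. Two things can change together between Week 52 and Week 56: the participant has stopped dulaglutide, and the participant may have eaten. Neither document records fasting status at Visit 801, so nothing collected separates the two.

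Visit 801 is the only scheduled off-drug laboratory visit after treatment. A reader of the by-visit lipid table will naturally take a Week 56 change as a withdrawal effect. The abnormality listing is exposed in two ways. A fed triglyceride above the upper limit at Visit 801 can appear as treatment-emergent. A fed high value at Visit 1 can make a genuine later elevation look pre-existing. A fed value above 400 mg/dL would also switch that participant's LDL from calculated to direct assay between visits.

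**Working it through.** The plan states no figure on this point, so there is none to reproduce. The check is a reading of the schedule, a trace through the SAP, and an illustration of size.

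**1. Schedule rows side by side (Protocol 1.3; Visits 2 and 4 are by telephone)**

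| Row | 1 | 3 | 5 | 6 | 7 | 8 | 9 | ET | 801 |
|---|---|---|---|---|---|---|---|---|---|
| Fasting visit | – | X | X | X | X | X | X | X | – |
| Fasting serum glucose | – | X | X | X | X | X | X | X | – |
| Lipid panel | X | X | – | – | X | – | X | X | X |

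The fasting row equals the fasting glucose row. The lipid panel is drawn without a fasting requirement at two visits, 1 and 801.

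**2. Trace through the SAP**
- Change from baseline: the baseline is normally Visit 3, which is fasting. Weeks 26 and 52 are then fasting against fasting, and Week 56 is possibly fed against fasting. If the Visit 3 value is missing, the baseline falls back to Visit 1, which is not a fasting visit.
- Model: it has visit and treatment-by-visit terms and an unstructured covariance if that converges, so Week 56 has its own mean and variance.
- Display: for laboratory values, Case 2 uses descriptive statistics for the by-visit change, takes only the treatment comparison from the model, and plans no within-arm test. The fed effect therefore shows in the descriptive Week 56 column.
- Abnormality listing: I read treatment-emergent as abnormal after a baseline period without that abnormality. A fed Visit 1 value can then affect status at any later visit, and a fed Visit 801 value affects status at that visit.

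**3. Illustration of size (assumed inputs; the documents give none)**

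Let d be the fed rise in triglycerides and f the share attending fed. With total cholesterol (TC) and HDL held constant and values in mg/dL, Friedewald gives LDL = TC − HDL − TG/5. The mean shifts are therefore:
- triglycerides: f × d
- calculated LDL: −f × d/5

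Assume mean triglycerides of 150 mg/dL and a rise of 10% to 30%:
- d = 0.10 × 150 = 15, up to 0.30 × 150 = 45 mg/dL.
- f = 1: triglycerides +15 to +45 mg/dL; LDL −15/5 = −3 to −45/5 = −9 mg/dL.
- f = 0.5: triglycerides +7.5 to +22.5 mg/dL; LDL −1.5 to −4.5 mg/dL.
- f = 0: no shift.

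**4. Effect on the dose contrast**

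The between-arm shift is (f for 1.5 mg − f for 0.75 mg) × d. It is 0 when the fed shares are equal. Even a gap of 60% against 40% would give 0.2 × 15 = 3 to 0.2 × 45 = 9 mg/dL for triglycerides and 0.6 to 1.8 mg/dL for LDL. Nothing in a randomised, blinded design points to such a gap.

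**The case against.** The strongest reply is that no stated objective is touched. The safety objective compares doses through 26 and 52 weeks, and the lipid samples at Visits 3, 7, 9 and ET are all fasting. SAP 4.8 leaves follow-up data out of the Week 26 safety analysis. Neither document sets a lipid-withdrawal objective. The fasting row was evidently built around fasting glucose, which is not measured at Visit 801, and a general safety blood draw there is a coherent choice. Display specifications are in a separate document (SAP Introduction), so a footnote on fasting may exist there. All of this stands, and it keeps the point small. It does not remove it, because the Week 56 outputs are planned and will be read.

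Three stronger readings are tempting, and the documents do not support them:
- **That the SAP pools fed and fasting values.** The model gives Week 56 its own mean, and the change baseline is normally the fasting Visit 3 value.
- **That the Week 56 table and listings are wrong.** Fasting at Visit 801 is not forbidden and the fed share is unknown. They can mislead; they are not shown to be wrong.
- **That all 585 randomised participants carry the artefact.** That number is a ceiling. The plan assumes 10% drop-out, and early leavers have Visit 801 about 4 weeks after ET rather than at Week 56. Those who stopped study drug early may by then be on other glucose-lowering therapy, which already complicates their values.

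**Conclusion.** The point holds as a minor design gap. Followed as written, the plan sets possibly fed Week 56 triglycerides and calculated LDL against a normally fasting baseline, and uses Visit 1 and Visit 801 triglycerides of unknown fasting status to decide treatment-emergent abnormality. What can go astray is the descriptive within-arm change at Week 56 and individual entries in the abnormality listing, with added noise in the dose comparison at that visit.

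A reader might infer that the 1.5 mg versus 0.75 mg comparison is biased. It is not biased in expectation, because the arms are randomised and blinded and fed attendance should balance. HbA1c, the sample size, and the Week 26 and 52 lipid changes are unaffected, apart from the rare baseline that falls back to Visit 1.

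The size cannot be taken from the documents. The range of 15 to 45 mg/dL for triglycerides and 3 to 9 mg/dL for LDL rests on an assumed 150 mg/dL, an assumed 10% to 30% fed rise, everyone attending fed, and constant total cholesterol and HDL. It shrinks in proportion to the share who fast anyway.

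**What to change.** **Protocol.** Mark Visit 801 in the Fasting visit row of the schedule and add it to the fasting text in 4.1, so that its lipid panel matches Visits 3, 7, 9 and ET.

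**SAP, for triglycerides and calculated LDL only.** Take baseline and treatment-emergent status from fasting visits, which leaves out Visit 1. Flag Visit 801 values drawn before the change as possibly non-fasting, or omit them from change from baseline. Keep total cholesterol and HDL at every visit: the mechanism does not concern them, and dropping the whole Visit 801 panel would discard usable data.

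**Cost.** One more fasting morning at a visit participants already attend. Under the schedule's existing rule, a participant who arrives unfasted may be called back within the visit window. A minor protocol amendment with ethics approval and a short SAP addition are needed. If the visits are already complete, the SAP flag alone is enough. Sample size and power do not change.
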